**Appendix K : Schedule of structured kangaroo care educational program (KC-EP) for nurses.**

**Venue: NICU, Conference Room, University Malaya Medical Centre**

Date/ Time	Pretest / Theory session	Date/ Time	Posttest / Practical Session (Morning session)	Date /Time	Posttest / Practical Session (Afternoon session)	Posttest after 7 th day
02.00 pm - 02.30 pm	Registration for kangaroo care educational program (KC-EP) - Pretest (QI)	08.00 am - 08.30 am	Registration for post-test after attended KC-EP for nurses	02.00 pm - 02.30 pm	Registration for post-test after attended KC-EP for nurses	- Post intervention Posttest (QI)  - Demonstrate (Checklist)
02.30 pm - 04.00 pm	Introduction of KC: - Define KC - KC physiology - KC benefits - KC indication & contraindication - KC guidelines and protocols	08.30 am - 10.00 am	KC hand-on workshop: - KC Ice-breaking - Demonstration - Question and Answer(QA)	02.30 pm - 04.00 pm	KC hand-on workshop: - KC Ice-breaking - Demonstration - Question and Answer(QA)	- Gift certificates to nurses who have pass and proficient in posttest knowledge and skills on KC.
04.00 pm - 04.30 pm	Tea Break	10.00 am - 10.30 am	Tea Break	04.00 pm - 04.30 pm	Tea Break	
04.30 pm - 06.00 pm	KC procedure - preparation infant- mother - equipment before, during and after the KC procedure (standing and sitting transfer) - recognize sign and symptoms of deterioration during and after KC procedure - charting the infant progress record - Question and Answer(Q&A)	10.30 am - 12.00 noon	Return demonstration of KC procedure: - Standing and sitting transfer - Question and Answer (Q&A)	04.30 pm - 05.00 pm	Return demonstration of KC procedure: - Standing and sitting transfer - Question and Answer(Q&A)	

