### **3.17 Method of Data Collection for Nurses**

The nurses were screened and recruited based on universal sampling. Method of data collection for nurses was similar to that for mothers, whereby, prior to the KC-EP for nurses, pretest data on nurses' perception, knowledge, and practice were collected using the KCQ tool in Questionnaire II. The data for nurses were collected within a 2 month period from 1st August 2018 to 30th September 2018 for the pretest-posttest groups of nurses. The researchers briefed the nurses and encouraged them to take part in the study by presenting verbally brief information to the head nurse in charge of the unit, with two forms of consent given to the nurses on the same day as the pretest program. All nurses who attended were recorded with their name, identification code number, date of attendance and signature in order to plan the date for their following posttest. To ensure confidentiality and privacy, each returning questionnaire was assigned an identification code number. The consent form together with the questionnaire was stamped, starting with nurse 01(N01), with the code number in the top right corner. If the nurses refused to continue with the study, they were instructed to notify the researcher and ask for a withdrawal. Upon receiving an application for withdrawal from the study, the researcher found and destroyed the questionnaire, which was submitted based on the code number. The pretest (Questionnaire II) was given to all nurses before the KC-EP was administered to them. The nurses were instructed to complete Questionnaire II, which took approximately 15 to 20 minutes to complete, without reference to any resources before the KC-EP session for nurses was conducted. Nurses were asked to return the questionnaires upon completion, with one copy of the informed consent. All nurses were advised to keep one copy of the informed consent for their records. Following the completion of the KC-EP, the nurses were told of the posttest sit after the 7th day of the pre-test and intervention program. The same structured Questionnaire II was administered to the nurses at the posttest. Data collection among nurses was conducted within the stipulated time.

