All 47 nurses needed to demonstrate KC skills, attitudes, and knowledge for practical evaluation and assessment. The knowledge, skills, and attitudes of nurses towards the implementation of KC were observed during the practical return-demonstration session to improve the quality care of preterm infants. The current research attempted to determine whether the nurses were more likely to support KC for the mother of a preterm infant. The marks were classified as pass or fail. The nurses received one (1) accredited certificate related to the KC course upon completion of the structured KC-EP course evaluations. A 6-point Continuous Professional Development (CPD) certificate recognized by the Malaysian Nursing Board was issued to all nurses attending the KC-EP; the KC-EP on knowledge, attitude, and skills was passed successfully. Examples of the KC-EP schedules for nurses are shown in (Appendix I & J). All of the data collected at the pretest was intended to assess nurses' previous knowledge on KC before they were introduced to the KC technique in the NICU setting. The questionnaire was collected before the KC-EP was delivered. The posttest for nurses was conducted on the 7th day after the KC intervention program(KC-EP). The nurses also answered the same set of questions in Questionnaire II and demonstrated their skills in relation to KC procedure: standing and sitting transfers with a checklist provided to evaluate their knowledge, skills and attitude regarding encouraging mothers to perform KC and continue breastfeeding,

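### Appendix K ties a certificate to passing the nurses' posttest while the pretest carries no stake, so the uncontrolled nurse change may partly reflect test motivation or wish to please

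*Combined protocol and SAP*

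**What the plan says.** Appendix K (nurses' schedule) has a column for the posttest after the seventh day. It holds three entries: the posttest questionnaire, the demonstration with checklist, and "Gift certificates to nurses who have pass and proficient in posttest knowledge and skills on KC".

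Section 3.17 describes the same occasion: "The nurses also answered the same set of questions in Questionnaire II and demonstrated their skills in relation to KC procedure". On grading it says only "The marks were classified as pass or fail". That sentence follows text on the practical return demonstration, and no pass mark is given. Two certificates are mentioned:

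- "The nurses received one (1) accredited certificate related to the KC course upon completion of the structured KC-EP course evaluations".
- A 6-point CPD "certificate recognized by the Malaysian Nursing Board was issued to all nurses attending the KC-EP". The same sentence goes on to say that the KC-EP was passed.

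The pretest has no such consequence: "All of the data collected at the pretest was intended to assess nurses' previous knowledge on KC".

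On identification, section 3.17 states "All nurses who attended were recorded with their name, identification code number, date of attendance and signature", in order to plan the posttest date. Sections 3.15.3 and 3.15.5 have the researcher deliver the KC-EP and collect the data at both times. Section 3.16 describes the nurse phase as one group with a pretest and a posttest. Section 2.5.2 puts evaluation of skills outside the scope of the study, although the checklist is completed.

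**The concern.** The third objective and H3 are answered by the difference between two administrations of Questionnaire II, about seven days apart, in the same nurses. Anything that differs between the two occasions, other than the KC-EP, enters that difference. Under Appendix K one such thing is the stake. A nurse filling in the form at registration gains nothing by answering well. A nurse filling it in at the posttest may believe that a certificate depends on it.

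For knowledge, the likely response is more effort and less readiness to admit doubt. Perception (section 3.10.1, Part I) and practice, which is self-rated comfort (Part III), have no right answer. There the risk is that a nurse known by name to the teacher shades her answers towards what was taught. No comparison nurses and no planned analysis would separate either effect from learning.

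**Working it through.** **1. The certificate rules side by side**

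| Source | Certificate | Condition |
|---|---|---|
| Appendix K | certificate on the posttest day | pass in posttest knowledge and skills |
| 3.17 | accredited course certificate | completion of the course evaluations |
| 3.17 | 6-point CPD certificate | issued to all attending, though the sentence also says the programme was passed |

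The documents do not say whether these are one, two or three certificates. Nor do they say whether the questionnaire score, the checklist or both decide them. Appendix K lists the checklist separately from the questionnaire, so its reference to posttest knowledge most naturally means the questionnaire. Section 3.17 can be read as grading the practical only.

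**2. A route from motivation to a higher knowledge score**

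Inputs from section 3.10.1, Part II: 20 items, 11 positive and 9 negative; 'not sure' = 1, 'false' = 2, 'true' = 3; negative items reversed by a rule that is not defined; a mean of 2.34 or more counts as good knowledge. Assumption: a nurse who guesses splits evenly between true and false.

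*Reading A: on negative items false = 3, true = 2, and 'not sure' stays at 1.*
- A guessed item is expected to score (3 + 2)/2 = 2.5, against 1 for 'not sure'.
- Each item moved adds 1.5/20 = 0.075 to the mean.
- All 'not sure' gives 1.00; all guessed gives 2.50.
- Items needed to go from 1.00 to the cut-off: (2.34 − 1.00)/0.075 = 17.9, so 18 of 20.

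*Reading B: the reversed score is 4 minus the raw score.*
- All 'not sure': (11 × 1 + 9 × 3)/20 = 38/20 = 1.90.
- All guessed: (11 × 2.5 + 9 × 1.5)/20 = 41/20 = 2.05, a rise of 0.15.
- Here a guess raises a positive item by 1.5 and lowers a negative item by 1.5, so the net effect depends on which items are guessed.

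If all 20 items move, the score rises without learning under both readings. The amount ranges from 0.15 to 1.50 according to the undefined reversal rule.

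**3. How large a shift would matter**

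The plan gives no effect size, SD or power for the nurses, so there is no figure to reproduce. Inputs: 46 + 1 = 47 nurses invited (section 3.7.3), all assumed to complete both tests; two-sided 5% level (section 3.19.1).

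- Paired comparison, shift detectable at 80% power: d = (1.960 + 0.842)/√47 = 0.41 SD of the within-nurse differences (0.42 by the exact noncentral t).
- Rejection rate with no programme effect and a non-programme shift d, from the noncentral t with 46 df and noncentrality d√47: 27% at 0.2 SD, 52% at 0.3 SD, 92% at 0.5 SD.
- Independent t-test, listed for nurses in Table 3.4 beside GLM and repeated measures: d = (1.960 + 0.842) × √(2/47) = 0.58 SD of the score for 80% power. By the normal formula the rejection rate is 16% at 0.2 SD and 31% at 0.3 SD.

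The two SD units differ, so the paired and independent figures are not directly comparable.

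**4. Direction for perception and practice**

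Both scales run from 1 to 5, with 5 as strong agreement or greatest comfort. Yet section 3.10.1 labels perception means of 2.77 and below as high perception, and practice means of 2.26 and below as high confidence. Answers shaded upward could therefore move a nurse into the unfavourable category.

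**The case against.** A reader might infer that Questionnaire II is the graded examination, and that part of any nurse gain is therefore effort. The documents do not support that. No questionnaire score is called a pass mark, and the 2.34 cut-off only separates good from poor knowledge. The pass-or-fail sentence in section 3.17 sits after the practical, and one certificate goes to everyone attending. Nothing shows that nurses changed how they answered. This stands, and it limits the point to a possible bias and an unresolved rule.

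A reader might also infer that all three nurse scores are biased in favour of the KC-EP. Appendix K names only knowledge and skills. For perception and practice the concern is ordinary wish to please, which would exist without a certificate, and the cut-offs leave its direction open. This stands too.

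The rejection rates are generic: they apply to any bias of that size in any 47-person before-after comparison and say nothing about this incentive. That is correct, so they serve only as a scale.

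Recording names with codes is not in itself a fault, since pairing the two tests needs a linked identifier. The certificate is also a smaller threat to H3 than the lack of a comparison group, and section 3.9 names infant weight gain and LOS as primary outcomes. Both remarks are fair. They bear on priority, not on whether an avoidable difference in stakes should be removed.

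**Conclusion.** The point holds in a limited form. Followed as written, Appendix K puts a one-sided incentive on at least the knowledge outcome, on the same occasion as the outcome questionnaire, and section 3.17 contradicts its rule. In an uncontrolled before-after comparison run by the teacher, the knowledge gain may partly reflect test motivation, and the perception and practice changes may partly reflect wish to please. The design cannot separate these from the KC-EP.

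The size is unknown. The 0.2 and 0.3 SD shifts are assumptions, and the guessing calculation rests on even guessing and on a reversal rule that the plan does not define. This is a worthwhile, cheap correction to a non-primary objective, not evidence that the nurse result is wrong.

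**What to change.** Reconcile section 3.17 with Appendix K so that the certificate rests on attendance and the observed skills checklist only. Skills are not a study outcome, so grading them leaves the three nurse scores free of a stake. Delete posttest knowledge from the certificate rule in Appendix K. State on the form that Questionnaire II is unmarked research data with no bearing on certification, and have it returned in a sealed envelope bearing the code needed for pairing. Appendix K already lists the questionnaire before the demonstration, so the order need not change.

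Sections 3.16 to 3.18 describe nurse data collection in August and September 2018 in the past tense. If the data are already collected, state what in fact decided the certificate, analyse 'not sure' responses separately at pretest and posttest, and report H3 as an uncontrolled before-after change.

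The cost is a few lines of wording and one small descriptive analysis. The downside is that the certificate no longer attests a written test.

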**Appendix L: Courses contents structured kangaroo care educational program (KC-EP) for mothers.**

 UNIVERSITY OF MALAYA	Course contents of Kangaroo Care Education Programme (KC-EP) for mother.
Educational Program Session (Participant)	All mothers in intervention group at neonatal intensive care unit (NICU) University Malaya Medical Centre (UMMC)
Course: Course Title: Medium of instruction Presenter :	Kangaroo Care Educationa Programme (KC-EP) Kangaroo Care Benefits for Premature Infant- Mother dyads and quality of care. Bahasa Malaysia and English [name]
Teaching materials/ Equipment	Laptop, LCD, white board, marker pen, lecture notes, showing video, pamphlets, booklet, infant dummy, baby sling, diapers, infant cap, all related forms applicable to the topic presentation and red & blue ball point.
Mode of teaching  Learning	Lecture-demonstration  Lecture (show and tell),practical (skill) & Question and Answer
Student learning time	Face to face (interpersonal communication): 1 hours Guide learning(theory):30 hours Assessment (practical) :30 hours
Presenter e-mail address	[name] [contact] @ [contact]
Theory & practical session: Day : Time : Venue :	Every Friday, Saturday and Sunday 10.00 am – 11.00 am. 12.00noon – 1.00pm or 3.00pm – 4.00pm & 5.00pm – 6.00pm Conference Room, Neonatal Intensive Care Unit, University Malaya Medical Centre, Klang Valley
General objective	At the end of the presentation the mothers will be able to have in depth understanding of kangaroo care in detail and demonstrate the procedure as well.
Specific objectives :	At the end of the presentation the mothers will be able to: 1) define term of kangaroo care (KC). 2) state the benefits of KC to infant-mother (breast feeding) 3) recognize sign and symptoms of deterioration among premature infant before, during and after the procedure 4) state the preparation before, during and after the KC procedure. 5) list the equipment for KC procedure; 5.1 infant 5.2 mother 6) demonstrate and return-demonstrate & charting the infant progress record by the nurses to mothers
Important dates (Primary and Secondary outcomes)	Pretest & posttest after 1 st month and 3 rd months of KC-EP for mothers.

**Appendix M (a) : Schedule of structured kangaroo care educational program (KC-EP) for mother's.**

Date / Time	Kangaroo Care Educational Program (KC-EP) for mother Venue : NICU, Conference Room, University Malaya Medical Centre Participant : All mothers in experimental group and nurses available in NICU
9.45 am - 10.00 am	Registration structured educational program (KC-EP) for mothers' - Pretest (experimental mother's group & nurses)
10.00 am - 10.20 am	Introduction of kangaroo care (KC) 1. What is kangaroo care? 1.1 Kangaroo care definition. 2. Who can perform kangaroo care? 2.1 indication and contraindication of kangaroo care. 3. When can mothers perform kangaroo care? 3.1 before, during and after kangaroo care procedure (instruments and observation needs). 3.2 indicate any abnormalities. 4. How do mothers perform kangaroo care? 4.1 showing videos on kangaroo care procedure. 4.2 show and tell how to perform and document in kangaroo care (KCRP booklet) 4.3 informative pamphlet. 4.4 equipment for kangaroo care procedure (infant & mother). 4.5 preparation before, during and after the kangaroo care procedure. 4.6 demonstrate the standing and sitting kangaroo care procedures. 4.7 charting the infant progress record by mother assisted by nurses * Question and Answer
10.20 am - 11.00 am	KC procedure preparation and Hand-on station 5. Why should mothers perform Kangaroo Care? 5.1 Benefits for babies; 5.2 Benefits for mothers; 6. How do mother recognize sign and symptoms of deterioration before, during and after KC procedure? 7. Health education on breastfeeding status (handwashing) 8. Demonstrate and return demonstration of KC technique * Question and Answer
11.00am	Tea break

**Appendix M(b) : Schedule of KC-EP (cont'd)**

Date / Time	Mother Structured Kangaroo Care Educational Program (KC-EP) Venue : NICU, Conference Room, University Malaya Medical Centre Participant : All mothers in intervention group and nurses available in NICU
11.45 am - 12.00 am	Registration structured kangaroo care educational program (mothers) - Pretest and intervention mother's group & nurses
12.00 am - 12.20 noon	Introduction of KC 1. What is Kangaroo Care (KC)? 1.1 definition of term KC 2. Who can perform Kangaroo care? 2.1 indication and contraindication of KC 3. When can mothers perform Kangaroo care? 3.1 pre, during and post KC technique (instruments and observation needs) 3.2 indicate any abnormalities 4. How do mothers perform Kangaroo care? 4.1 showing a videos on KC technique/procedure 4.2 show and tell how to perform and document it in KC diary provided for mothers (KCRP booklet) 4.3 informative pamphlet 4.4 equipment for KC procedure e. g infant & mother 4.5 preparation before, during and after the KC technique 4.6 demonstrate the standing and sitting procedure 4.7 charting the infant progress record/by mother assisted by nurses * Question and Answer
12.20 noon - 01.00 pm	KC procedure preparation and Hand-on station 5. Why should mothers perform Kangaroo Care? 5.1 Benefits for babies; 5.2 Benefits for mothers; 6. How do mother recognize sign and symptoms of deterioration before, during and after KC procedure ? 7. Health education on breastfeeding /feeding status. 8. Demonstrate and return demonstration of KC technique * Question and Answer
01.00pm	Tea break

### Appendix M(c): Schedule of KC-EP (cont'd)

Date / Time	Mother Structured Educational Program in Kangaroo Care (KC-EP) Venue: NICU, Conference Room, University Malaya Medical Centre Participant: All mothers in the experimental group and nurses available in NICU
2.45 pm - 03.00 pm	Registration structured KC Educational Program for mothers'or KC-EP - Pretest and intervention mother's group & nurses
03.00 pm - 03.30 am	Introduction of KC 1. What is Kangaroo Care(KC)? 1.1 definition of term KC 2. Who can perform Kangaroo care? 2.1 indication and contraindication of KC 3. When can mothers perform Kangaroo care? 3.1 pre, during and post KC technique (instruments and observation needs) 3.2 indicate any abnormalities 4. How do mothers perform Kangaroo care? 4.1 showing a videos on KC technique/procedure 4.2 show and tell how to perform and document it in KC diary provided for mothers (KCRP booklet) 4.3 informative pamphlet 4.4 equipment for KC procedure e. g infant & mother 4.5 preparation before, during and after the KC technique 4.6 demonstrate the standing and sitting procedure 4.7 charting the infant progress record/by mother assisted by nurses * Question and Answer
03.30 pm - 04.00 pm	KC procedure preparation and Hand-on station 5. Why should mothers perform Kangaroo Care? 5.1 Benefits for babies; 5.2 Benefits for mothers; 6. How do mother recognize sign and symptoms of deterioration before, during and after KC procedure? 7. Health education on breastfeeding/feeding status 8. Demonstrate and return demonstration of KC technique * Question and Answer
04.00 pm	Tea Break

[figure not shown]
**Appendix M(d) : Schedule of KC-EP D (cont'd)**

Date / Time	Kangaroo Care Education Programme (KC-EP) Venue : NICU, Conference Room, University Malaya Medical Centre Participant : All mothers in experimental group and nurses available in NICU
4.45 pm - 05.00 pm	Registration Kangaroo Care Education Programme (KC-EP) for mothers. - Pre-test and experimental mother's group & nurses
05.00 pm - 05.20 pm	Introduction of KC 1. What is Kangaroo Care (KC)? 1.1 definition of term KC 2. Who can perform Kangaroo care? 2.1 indication and contraindication of KC 3. When can mothers perform Kangaroo care? 3.1 pre, during and post KC technique (instruments and observation needs) 3.2 indicate any abnormalities 4. How do mothers perform Kangaroo care? 4.1 shows a video on KC technique/procedure 4.2 show and tell how to perform and document it in KC diary provided for mothers (KCRP booklet) 4.3 informative pamphlet 4.4 equipment for KC procedure e. g infant & mother 4.5 preparation before, during and after the KC technique 4.6 demonstrate the standing and sitting procedure 4.7 charting the infant progress record/by mother assisted by nurses * Question and Answer
05.20 pm - 06.00 pm	KC procedure preparation and Hand-on station 5. Why should mothers perform Kangaroo Care? 5.1 Benefits for babies; 5.2 Benefits for mothers; 6. How do mother recognize sign and symptoms of deterioration before, during and after KC procedure? 7. Health education on breastfeeding and handwashing 8. Demonstrate and return demonstration of KC technique * Question and Answer
04.00pm	Tea break

[figure not shown]
## Appendix N: Handwashing steps

[figure not shown]
Wet hands with water

[figure not shown]
apply enough soap to cover all hand surfaces.

[figure not shown]
Rub hands palm to palm

right palm over left dorsum with interlaced fingers and vice versa

[figure not shown]
palm to palm with fingers interlaced

backs of fingers to opposing palms with fingers interlocked

rotational rubbing of left thumb clasped in right palm and vice versa

[figure not shown]
rotational rubbing, backwards and forwards with clasped fingers of right hand in left palm and vice versa.

Rinse hands with water

dry thoroughly with a single use towel

use towel to turn off faucet

...and your hands are safe.

